#### **Relevance to VA Care:**

Given the numbers of Veterans with sub-optimal cardiovascular control, developing models of care to best help this population is critical to the VHA mission. Peer support may provide a needed link between Veterans and available VHA clinical services and serve as a community-clinic liaison to strengthen connections to community-based resources. Utilizing trained peers may be one mechanism to improve health among Veterans. However, much research is needed to determine the role and effectiveness of peer support. The VHA has a well-developed evidenced-based Health Promotion and Disease Prevention (HPDP) program. Expanding the reach of this program by the use of peer health coaches has the potential to provide cost-effective health coaching.

Unique and innovative features of the Vet-COACH intervention include:

- Veterans will not have to travel to a class or clinic, thereby increasing participation in self-management education, enhancing recruitment and retention.

- Veterans will be more comfortable in their homes during the health coaching calls, and therefore more able to participate actively in learning activities and develop trusting relationships with the Veteran peer health coaches.
- Peer health coaches will be able to role-model and observe participants in practicing self-management behaviors (e.g. managing medications).
- Peer health coaches will be able to make suggestions that household members be enlisted to provide support for Veterans.
- Peer health coaches will be able to link Veterans to pre-existing programs (e.g. disease self-management classes, MOVE, home tele-monitoring).
- Peer health coaches have access to PACT teams and can assist Veterans engagement in care.

The proposed research has the potential to contribute to the VHA mission to provide patient centered care, and also to develop, facilitate and integrate peer support into PACT teams. This proposal directly targets improving a Veteran-centric health care model to help Veterans navigate the health care delivery system and receive coordinated care. By providing training curricula and data on the effectiveness of peer health coaches, our goal is to present VHA policymakers with evidence regarding peer health coaches work to decrease CV risk and improve Veteran health.

### 3.0 Objectives

- Describe the study's purpose, specific aims, or objectives.
- State the hypotheses to be tested.

Cardiovascular disease (CVD) is the leading cause of mortality among Veterans, and sub-optimal risk factor control is an important mechanism for the continued prevalence of CVD. Despite clinic-based programming that includes nurse care management, pharmacy support, telephone care programs and intensive quality improvement efforts, CVD risk factors remain sub-optimally controlled among Veterans. Modifiable CVD risks include hypertension, hyperlipidemia (HLD), obesity and tobacco use. These conditions are common, often co-exist, and are amenable to behavior change and disease self-management interventions. Among Veterans with hypertension, 25% have poor control (as defined by a blood pressure of >140/90 mmHg). Similar to the US population, the majority of Veterans are overweight or obese, are sedentary and eat unhealthy diets. Over one quarter of Veterans smoke. To improve health and decrease CVD morbidity and mortality, CVD risk reduction is an important issue facing VHA and other U.S. health systems.

There is a growing literature about the positive health benefits of peer support on health outcomes and health behavior change. Previous studies of peer support in non-VHA populations report significant improvement in hypertension control and CVD risk reduction. There are several peer support titles, including peer coaches, navigators, and community health workers (CHWs), with the common characteristic of sharing life experiences and social background with the patients being served, and promoting health by providing education, assistance, motivation and social support. Several models of peer support have been tested in

VHA, but have primarily targeted single conditions, e.g. diabetes or among Veterans with mental health conditions.

### Specific Aims:

1. Test the effectiveness of a peer health coach intervention for improving health outcomes for Veterans with multiple CVD risks in a randomized controlled trial. The primary outcome is a reduction in systolic blood pressure (SBP) from baseline to follow-up at 1 year. Secondary outcomes include change in cardiovascular risk, as measured by the Framingham Risk Score, other cardiovascular risks (tobacco use, lipids) and health related quality of life. Using administrative data at 1 year following randomization, we will examine healthcare utilization, hospitalizations, and emergency room visits.
2. Assess the effects of a peer health coach intervention on intermediate outcomes that are intervention targets including social support, patient activation, *patient/provider communication* and health behaviors (e.g. medication adherence, physical activity, nutrition, *alcohol use, and stress management*).
3. Assess the cost of the intervention to inform feasibility for future studies.
4. Determine Veteran and staff satisfaction with the intervention and identify barriers and facilitators to adoption.

The recent VHA medical home model initiative, the Patient Aligned Care Team (PACT), is an ideal setting to test peer support, as this social support model aligns with the PACT focus on team-based, patient-centered, and comprehensive care. The PACT team includes a primary care provider, an RN care manager, and a LPN; as well as support staff including pharmacists and Health Promotion and Disease Prevention (HPDP) staff. The focus of the HPDP program is to support chronic disease self-management and promote healthy lifestyle choices. **Trained Veterans working as peer health coaches may be a mechanism to expand the reach of the PACT team by (1) providing brief health education messages based on HPDP program materials, (2) acting as a community-clinic liaison to create stronger linkages between primary care and community resources and (3) by linking Veterans to community-based resources for healthy lifestyle choices.** The overall goal of this study is to test the effectiveness of a peer health coach intervention (**Vet-COACH “Veteran peer Coaches Optimizing and Advancing Cardiac Health”**) to promote health behavior change among Veterans with multiple CVD risk factors with a 4-year hybrid type 1 implementation study. To target a high risk population, we will focus on Veterans with poorly controlled hypertension and at least one other CVD risk.

Integrating peer health coaches into the PACT primary care team may improve the VA's ability to provide community outreach to Veterans. CVD risk reduction provides an ideal target for intervention given the prevalence of modifiable risks among Veterans. The proposed study will increase understanding of the utilization of peer support within PACT teams. If this study proves the main hypothesis, this evidence-based support model could be tested more widely among Veterans with other chronic conditions to improve health outcomes.

## 4.0 Resources and Personnel

- Include where and by whom the research will be conducted.
- Provide a brief description of each individual's role in the study. Be sure to indicate who will have access to protected health information and who will be involved in recruiting subjects; obtaining informed consent; administering survey/interview procedures; and performing data analysis.
- If applicable provide information on any services that will be performed by contractors including what is being contracted out and with whom.

**N/A**

- If applicable provide information on any Memoranda of Understandings (MOUs) or Data Use Agreements (DUAs) that are being entered into including with whom and for what reason.

## 5.0 Study Procedures

## 5.1 Study Design

- Describe experimental design of the study. Include sequential and/or parallel phases of the study, including durations, and explain which interventions are standard of care.
- Include a description of how anticipated risk will be minimized and include an analysis of risk vs. potential benefit.
- Provide description of the study population (delineate all categories of subjects – patients, providers, family members, employees, etc.). Include anticipated enrollment numbers
- As applicable, provide information on any added protections for vulnerable populations.
- If applicable include information on data and specimen banking.

### Study design overview:

We propose a randomized controlled trial to evaluate the effectiveness of **Vet-COACH**, a peer health coach program to control hypertension and reduce CVD risk among Veterans. The original program incorporated home visits by peer health coaches to deliver health education, counseling and goal setting support. Due to safety concerns and social distancing restrictions stemming from the COVID 19 pandemic, the program has transitioned to conducting all health coaching encounters, as well as enrollment and exit visits, via phone. This transition was implemented under IRB approval of the miscellaneous memo submitted at the beginning of the pandemic. These changes to conduct all health coaching encounters and exit surveys over the phone will be permanent for the remainder of the study. Our operations partners from NCP have developed extensive patient educational materials that will be used for the current study. We will train the peer health coaches to provide brief educational messages and link Veterans to existing clinical services at VHA, including their primary care PACT teams and community based programs. The main outcome will be a reduction in systolic blood pressure. Secondary outcomes are cardiovascular risk, as measured by the Framingham Risk Score (FRS), health care utilization and intermediate behavioral outcomes including patient activation, social support and health behaviors (e.g. diet and physical activity, medication adherence). *We will randomize a total of 200 individuals to the intervention group and 200 individuals to the control group.*

Our study design has limitations. Because of the nature of the intervention, we are unable to blind treatment assignment. The PI and [name] will provide overall supervision to the peer coaches. This model is necessary for program development. Because the intervention is being conducted at two sites, we are not proposing an economic evaluation to estimate cost-effectiveness, in part because such data would be of limited generalizability. Positive findings will lead to a larger multi-site trial that would include a cost-effectiveness analysis. These limitations are more than balanced by the strengths of this proposal. The proposed project is a prospective, randomized controlled trial that examines important outcomes with statistical power to detect clinically meaningful differences.

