**Enrollment and randomization:**

**a) Enrollment and exit visits**

The research coordinators will interview participants during the enrollment and exit visits over the phone. If a participant expresses completion of the exit survey over the phone would pose difficulties for them, staff will provide the option to complete and return the exit survey by mail. If the participant agrees, staff will mail a copy of the exit survey with a postage-paid return envelope to mail the completed survey to the HSR&D office. Study staff in possession of a VA-issued flip phone will use it to conduct the call. Study staff who do not have a VA phone or laptop will use their personal smart phone and conduct the call using the Doximity app. Scheduled participants will be mailed a letter prior to their enrollment visit that will confirm the date, time, and location of their appointment and a brief summary of what will be covered in the visit and program. The baseline enrollment visit and exit call will include blood pressure measurements and labs (lipids). If there are no lipid panel results in CPRS dated within 12 months prior to the baseline/enrollment date or 3 months prior to the exit visit date, the PI will order a lipid panel test. If a participant moves out of the Puget Sound area and/or receives lipid test results from a non-VA provider or clinic, we will request they send the lipid panel test results from the non-VA lab or VA lab in another state to the Puget Sound VA Primary Care Clinic via mail or secure fax. This is already done by VA patients who may get bloodwork at a non-VA facility. These results would be used as the lipid measurements typically collected at the exit visit. [name] (study coordinator and phlebotomist) will conduct the blood draw with participants completing the enrollment and/or exit visit with her. [name] has completed all the required trainings and coursework to conduct blood draws at the VA Puget Sound. Any results flagged as high will be reported by the PI to the participant's PCP -- either as an addendum to the research enrollment note or as an alert to the PCP if they are not enrolled in the study -- using the following statement: "We ordered a lipid panel test as part of screening or follow up for the Vet-Coach research project. Your patient may or may not participate in this study." Three blood pressure measurements will be collected by the research coordinators at intervals during the enrollment call. For BP measurement, after the patient has sat comfortably for 5 minutes, three BP consecutive measures are obtained and then averaged per NHANES protocol. All BP measurements will be performed with electronic, upper arm cuffs. The average BP must be  $>150/90$  mm Hg at the time of the data pull for Veterans to be eligible for the study. We will attempt to schedule enrollment visits within a week of their most recent primary care visit to recruit Veterans with uncontrolled hypertension. Height and weight will be measured at baseline and weight will be measured at exit. Measures collected include: chronic disease self-management behaviors, health history, health care access, and health care utilization. Urgent issues will be referred immediately to the PI. The PI will contact the PCP for urgent issues to ensure appropriate follow-up.

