Recommendations for potential health action plans, based on national guidelines and specific to the individual risk factor and patient motivation, will be generated at the enrollment visit. Using the results of the baseline assessment, the peer health coach will collaboratively develop an action plan with the Veteran. The protocols specify education content, Veteran skill development goals, participant and Veteran health coach actions. All Veterans will receive the five required education modules, including high blood pressure, medication adherence, physical activity, nutrition, and improved communication with medical team/physician (Table 2). The peer health coach will have participants prioritize their goals, ask what they would like to prioritize for their next call, and develop a goal-directed action plan [where the Veteran identifies a health related goal and decides how much time, when and how often they are going to complete the behavior (e.g. walk 10 minutes per day OR take my blood pressure pills every morning)], along with an assessment of how confident they feel in being able to complete the behavior. We will assess goal setting and goal completion rates in the Action Plan for the intervention participants. The peer health coach will document the skill or goal that was the primary focus for each call and the self-management strategies that were highlighted during that call on an encounter form. As progress toward the first goal is important for long-term motivation, a telephone follow up will occur 2 weeks after the first call. Blood pressure will be measured by the peer health coach at each call with a total of one blood pressure measurement at each call. The readings, if elevated, will be reviewed by the study coordinators and given to the provider. We will record these blood pressure readings in study data and use them to provide participant and PCP feedback. They will not be used as outcomes measures because we will not have equivalent data for the control participants. Initial and randomly selected phone calls with Vet-Coaches will be audio-recorded to ensure fidelity. Each Vet-Coach will audio-record initial calls until the PI deems they have met proficiency standards. After initial proficiency standards are met, each Vet-Coach will continue audio-recording of randomly-selected calls to ensure ongoing proficiency. Audio recordings will be collected using secure, VA approved digital recorders or recording software. Recordings and recording devices will be stored and transported in locked security bags to the VA Puget Sound office location every two weeks at study staff meetings. Audio recordings will then be uploaded to the secure, electronic folder on the VA server.

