## 5.5 Study Evaluations

- Describe all evaluations to be conducted (including screening; tests/questionnaires that will be administered; any procedures that subjects will be required to complete) and data collection methods.

Include materials as an appendix or separate attachment. Only refer to attachments as A, B, etc. Do not refer to version #'s or dates of versions. During the course of the study, changes in the attachments will require IRB approval; however, those changes may not require a revised protocol.

The sources of data for this project will be participant interviews and medical records. The participant interviews will be collected specifically for this project while the medical record data will be obtained from existing sources. In order to evaluate the effectiveness of the proposed intervention, the study will administer baseline and exit interviews, conduct limited physical examinations where blood pressure, height and weight are measured, and, if needed, we will request the primary care provider order a blood test for potential participants. The proposed interview and limited physical exam will be administered at baseline and after the intervention period and will be conducted by study coordinators or research assistant. Only the study personnel will have access to any personally identifiable health information.

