### **Primary and secondary outcomes**

The primary outcome measures will be systolic blood pressure. At the baseline visit and the final 12 month exit call, the study staff will ask the participant to measure blood pressure three times. At the time of scheduling, study staff will ask if the participant has a blood pressure monitor and/or scale in their possession. If the participant does not have a monitor or scale, staff will mail them one from the VA office. The mean value for these readings will be used for the baseline and exit measurements, respectively.

Secondary outcomes will include Framingham Risk Score (FRS), individual CVD risks (BMI, LDL-c, tobacco use), health care utilization and health-related quality of life. A 10-year risk of total CVD (including myocardial infarction, angina, coronary revascularization, stroke, congestive heart failure and peripheral arterial disease) will be determined according to FRS algorithms, which include age, total and high-density lipoprotein-cholesterol, systolic blood pressure, treatment for hypertension, diabetes, and cigarette smoking. Individual components of this risk score are targets of the intervention (hypertension, hyperlipidemia, and smoking). The FRS algorithm has good predictive validity for CHD events (c statistics 0.74 and 0.77 for men

and women, respectively). Health care utilization will include outpatient visits, emergency department visits, and hospitalizations. Health care utilization will be obtained from VA administrative data and by participant self-report to capture non-VA health care utilization. Health-related quality of life will be measured by the Medical Outcomes Study 12-item measure, the SF-12. Two composite scales will be used to measure physical health (the physical component summary) and mental health (mental health component summary).

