### Measuring Intervention fidelity

*Fidelity will be assessed to a) identify areas of needed improvement for ongoing remediation for the peer coaches through review of audio recordings (Section C.4.2); b) provide qualitative description of fidelity and needed changes to peer coaches at least quarterly (Section C.4.2); and c) include in the quantitative models to determine relationship between fidelity and outcomes (Section C.7.3). We will develop a manual for implementation of the intervention, very similar to our manual for our diabetes self-management trial (Appendix 3 of attached IIR). This manual consists of required and optional educational modules and educational materials that will be provided to the participant for each topic. To assess if participants received the*

*scheduled phone calls, the total number of phone calls will be recorded for each participant. Prior to study initiation and on a quarterly basis, peer support counselors must demonstrate competence in delivering content with fidelity ( $\geq 80\%$  of components). We will require the peer health coaches to complete an encounter form for each intervention visit; which will consist of a checklist of required modules and if they were delivered. We have developed encounter forms for our current CHW study that will be adapted for the current study. The study coordinators will abstract participant records to assess whether each client received the interventions specified by protocols. Study staff (RA, study coordinators, or Co-I) will also directly review audio recordings of one call per quarter to assess intervention fidelity. Fidelity will be measured using an observation form, and feedback will be given to each Vet-Coach. Monthly control reports will ensure that each participant received the required components of the intervention.*

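### Exit assessors can know the treatment arm and nothing in the plan prevents it; the reason given for not blinding does not cover them

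*Protocol*

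**What the plan says.** Among its limitations, the protocol (5.1, Study design overview) says: "Because of the nature of the intervention, we are unable to blind treatment assignment". It does not separate participants, coaches and outcome assessors.

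On the exit contact, the protocol says:
- Enrollment and exit visits: "The research coordinators will interview participants during the enrollment and exit visits over the phone".
- 5.5 Study Evaluations: the interview and limited examination, which includes blood pressure, "will be administered at baseline and after the intervention period and will be conducted by study coordinators or research assistant". Table 3 lists the RA for the exit call.
- Primary and secondary outcomes: "At the baseline visit and the final 12 month exit call, the study staff will ask the participant to measure blood pressure three times". The mean of the readings is the exit value.
- Specific Aim 4: satisfaction with the program is asked at the exit interview. No order of questions is given.

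On intervention-arm material, it says:
- Visit content and development of a health action plan, on the coaches' blood pressure readings: "The readings, if elevated, will be reviewed by the study coordinators and given to the provider". The section adds that controls have no equivalent data.
- Measuring Intervention fidelity: "The study coordinators will abstract participant records to assess whether each client received the interventions specified by protocols" and "Study staff (RA, study coordinators, or Co-I) will also directly review audio recordings of one call per quarter to assess intervention fidelity".
- 6.0 Reporting: coordinators receive the encounter forms and detach the cover sheets that carry names.

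The only masking described is concealment of the randomization sequence and, in the qualitative work, blinding to responder status. The SAP adds no masking of outcome assessment. Its section 5 takes blood pressure from the medical record when no exit visit was scheduled.

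**The concern.** An intervention of this kind cannot be hidden from those who receive or deliver it. It does not follow that the person making a single call at 12 months must know the arm, and the protocol gives no separate reason why that person should.

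An assessor who knows the arm can, without intending to, be stricter about the rest period in one arm, give more reminders on technique, or react differently to a high reading. For the interviewer-administered Aim 2 scales (self-reported adherence, diet, activity, alcohol use, stress management), the assessor can probe or accept answers differently. These scales are at least as exposed as blood pressure, since they rest on a conversation and not on a device.

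The effect sought is small: 4 mmHg in the hypothesis (Protocol 5.6; SAP section 6) and 5 mmHg in the power calculation. A differential of 1 to 2 mmHg would be 25-50% of the former (1/4, 2/4) and 20-40% of the latter (1/5, 2/5).

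**Working it through.** **Step 1: who does what.**

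| Task | Coordinators | RA |
|---|---|---|
| Exit interview | yes (Enrollment and exit visits; 5.5) | yes (5.5; Table 3, exit call) |
| Exit examination, including blood pressure | yes (5.5) | yes (5.5) |
| Review of elevated coach readings | yes | not named |
| Checking of delivery records | yes | not named |
| Receipt of named encounter forms | yes (6.0) | not named |
| Review of call recordings | one of three alternatives | one of three alternatives |

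Coach readings and encounter forms arise only in the intervention arm, so handling one for a named participant reveals that participant's arm. Coordinators meet such material routinely. The RA is named only as one possible reviewer of recordings. In addition, individual participants' coaching issues are discussed at bi-weekly study-team meetings (Visit content section), and the documents do not exclude exit assessors from these.

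**Step 2: reproduce the plan's own figure, so that the standard error below has the same basis.** Inputs from Study power and sample size: SD 14.2 mmHg, difference 5 mmHg, two-sided alpha 0.05, power 80%, provider ICC 0.015 with cluster size 5, coach ICC 0.007 with cluster size 35, attrition 15%.
- Per arm before clustering: 2 × (14.2 × (1.960 + 0.842)/5)² = 126.6, rounded up to 127.
- Provider design effect, both arms: 1 + 4 × 0.015 = 1.06.
- Coach design effect, intervention arm only: 1 + 34 × 0.007 = 1.238.
- Completers: 127 × (1.06 + 1.06 × 1.238) = 301.3. Divided by 0.85 this is 354.4, against 354 stated. Combining the two effects additively gives 352.3.

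**Step 3: standard error of the arm difference.** I take 170 completers per arm (85% of 200).
- With the plan's clustering, additive form: SE = 14.2 × √((1.06 + 1.298)/170) = 1.67 mmHg.
- With a common design effect D in both arms, SE = 14.2 × √(2D/170): D = 1.0 gives 1.54 and D = 1.3 gives 1.76. This range brackets the plan's average of 2.358/2 = 1.18.

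**Step 4: type I error under an assumed bias.** Let b be the average between-arm shift over all analysed participants, with no true effect. Then the two-sided type I error is Φ(b/SE − 1.96) + Φ(−b/SE − 1.96).

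| Assumed b (mmHg) | SE 1.67 | SE 1.76 to 1.54 |
|---|---|---|
| 0 | 5% | 5% |
| 0.5 | 6% | not computed |
| 1 | 9% | 8.8% to 10.0% |
| 2 | 22% | 20.7% to 25.5% |
| 3 | 43% | not computed |

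Example: b = 2 and SE = 1.67 give b/SE = 1.196, and Φ(−0.764) + Φ(−3.156) = 0.222 + 0.001 = 0.223.

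The documents supply no value for b. If a fraction f of exit values comes from the medical record, a handling difference h on the remaining exits contributes only b = (1 − f) × h.

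**The case against.** The strongest objection is that staff do not take the phone readings. The participant, who is unblinded, uses an electronic upper-arm cuff while staff prompt. The protocol also fixes five minutes of sitting and three averaged readings, so an extra reading would be a deviation. This stands in part. It narrows the assessor's influence to prompting and recording, and it shows a second route, self-measurement by an unblinded participant, that masking the assessor leaves untouched. It does little to protect the interview scales, although surveys can be returned by mail if a phone survey would be difficult. LDL-c, VA utilization and pharmacy-based adherence do not depend on the interviewer.

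A reader might infer that the assessor does know the arm. The documents do not go that far. They name roles, not individuals; they list recording reviewers as alternatives; and the fidelity section provides for one call per quarter. What they support is that the assessor can know.

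A reader might also infer that masking needs no extra staff. That is plausible, since the alternatives listed for recording review and the RA's place in Table 3 leave room to divide tasks. It cannot be checked, because the personnel pages were not available for this review. The protocol also describes a coordinator who doubles as phlebotomist at enrollment and exit visits, so reallocation may not be free.

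Finally, lack of blinding is already declared as a limitation, and the trial is under way: the SAP gives enrollment as 2017-2021 and describes blood pressure measurement in the past tense. Both points are correct. The declaration does not mention assessors, however, and the timing affects which part of the remedy still applies.

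**Conclusion.** The point holds in a limited form. The overlap of roles is documented, no safeguard keeps the exit assessor unaware of the arm, and the reason given for not blinding does not apply to that person. The inference that the assessor can know the arm is strong for coordinators and weaker for the RA.

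The size is conditional. An average differential of 1 mmHg would raise type I error to about 9-10%, and 2 mmHg to about 21-26%. These figures assume that bias, no true effect, SD 14.2, 170 completers per arm and a design effect of 1.0 to 1.3. The same arithmetic would apply to bias from any source, so it shows sensitivity and is not evidence that bias of this size occurred.

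It would also be wrong to infer that masking the assessor would clear the primary outcome of bias. Self-measurement, record-based values and disclosure by participants would remain. Masking is worth doing as an inexpensive partial improvement. It changes no sample size, alpha or power figure.

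**What to change.** For exits still to be done:
- **Study design overview:** limit the statement that blinding is not possible to participants and coaches, and say separately whether exit assessors are masked.
- **Enrollment and exit visits, and 5.5:** where existing staffing allows, give each exit call to a staff member who has not handled that participant's recordings, encounter forms or coach readings, working from a call list without arm.
- **Exit form:** record the three blood pressure readings first, place satisfaction and coaching questions last, and have the assessor note whether and when the arm became known.
- **Measuring Intervention fidelity:** leave recording review to the co-investigator or to a coordinator who does not make that participant's exit call.

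For exits already done, state that assessors were not masked, and list this together with participant self-measurement as a limitation.

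The cost is a short protocol edit, a call list without arm, a reordered form and some constraint on scheduling. Some participants will still disclose their arm. Because the change comes mid-trial, the data will mix masked and unmasked exits, so the date of the change should be recorded and reported.
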